Subgroups	Standard care	PCT	CRP	Effect estimate (95% CI)	PCT vs. Standard care	CRP vs. Standard care
	N; mean(sd)	N; mean(sd)	N; mean(sd)		Adjusted interaction effect (95% CI)	Adjusted interaction effect (95% CI)
Community-acquired pneumonia (CAP)						
	1					
	2					
Hospital-acquired pneumonia (HAP)						
	1					
	2					
Urinary tract infection (UTI)						
	1					
	2					
Intra-abdominal infection						
	1					
	2					
Infection with positive blood culture						
	1					
	2					
Severity (SOFA/APACHE II)						
	1					
	2					

ADDITIONAL ANALYSES

Table 25: Summary of total duration of antibiotic treatment during the intervention phase only by treatment group

	Standard care	PCT	CRP	PCT vs. Standard care Adjusted mean difference (95% CI)	CRP vs. Standard care Adjusted mean difference (95% CI)
Duration of antibiotic treatment (days)					
N	xx.xx	xx.xx	xx.xx		
Mean (SD)	xx.xx	xx.xx	xx.xx		
Median (IQR)	xx.xx	xx.xx	xx.xx		
Missing	xx.xx	xx.xx	xx.xx		

Table 26: Summary of total Daily Defined Dose (DDD) from randomisation to 28 days by treatment group

	Standard care	PCT	CRP	PCT vs. Standard care Adjusted mean difference (95% CI)	CRP vs. Standard care Adjusted mean difference (95% CI)
Daily Defined Dose (DDD) to 28 days (days)					
N	xx.xx	xx.xx	xx.xx		
Mean (SD)	xx.xx	xx.xx	xx.xx		
Median (IQR)	xx.xx	xx.xx	xx.xx		
Missing	xx.xx	xx.xx	xx.xx		

Table 27: Summary of total Daily Defined Dose (DDD) during the intervention phase only by treatment group

	Standard care	PCT	CRP	PCT vs. Standard care Adjusted mean difference (95% CI)	CRP vs. Standard care Adjusted mean difference (95% CI)
Daily Defined Dose (DDD)					
N	xx.xx	xx.xx	xx.xx		
Mean (SD)	xx.xx	xx.xx	xx.xx		
Median (IQR)	xx.xx	xx.xx	xx.xx		
Missing	xx.xx	xx.xx	xx.xx		

Table 28: Baseline demographic characteristics comparing pre-COVID participants versus participants recruited during COVID

Characteristic	Pre-COVID	During Covid	Total	P-Value
Age (years)				
N	xx.xx	xx.xx	xx.xx	x.xx
Mean (SD)	xx.xx	xx.xx	xx.xx	
Median (IQR)	xx.xx	xx.xx	xx.xx	
Missing	xx.xx	xx.xx	xx.xx	
Gender				
Male	n (%)	n (%)	n (%)	x.xx
Female	n (%)	n (%)	n (%)	
Missing	n (%)	n (%)	n (%)	
Critical care admission category				
Medical	n (%)	n (%)	n (%)	x.xx
Elective surgical	n (%)	n (%)	n (%)	
Emergency surgical	n (%)	n (%)	n (%)	
Other	n (%)	n (%)	n (%)	
Missing	n (%)	n (%)	n (%)	
Origin				
Emergency department	n (%)	n (%)	n (%)	x.xx
Emergency admissions unit	n (%)	n (%)	n (%)	
Medical ward	n (%)	n (%)	n (%)	
Surgical ward	n (%)	n (%)	n (%)	
Another critical care unit	n (%)	n (%)	n (%)	
Other	n (%)	n (%)	n (%)	
Missing	n (%)	n (%)	n (%)	
Core body temperature (°C)				
N	n (%)	n (%)	n (%)	x.xx
Mean (SD)	n (%)	n (%)	n (%)	
Median (IQR)	n (%)	n (%)	n (%)	
Missing	n (%)	n (%)	n (%)	
White cell count (x10⁹/L)				
N	xx.xx	xx.xx	xx.xx	x.xx
Mean (SD)	xx.xx	xx.xx	xx.xx	
Median (IQR)	xx.xx	xx.xx	xx.xx	
Missing	xx.xx	xx.xx	xx.xx	
Infection acquirement				
Community acquired	n (%)	n (%)	n (%)	x.xx
Hospital acquired	n (%)	n (%)	n (%)	
Missing	n (%)	n (%)	n (%)	
Site of infection causing sepsis*				
Respiratory tract	n (%)	n (%)	n (%)	x.xx

If yes above, was it pneumonia	n (%)	n (%)	n (%)	x.xx
If yes above (pneumonia), was it ventilator related	n (%)	n (%)	n (%)	x.xx
Central nervous system	n (%)	n (%)	n (%)	x.xx
Skin and soft tissue	n (%)	n (%)	n (%)	x.xx
Is yes above, was it a surgical site infection	n (%)	n (%)	n (%)	x.xx
Central line related infection	n (%)	n (%)	n (%)	x.xx
Intra-abdominal	n (%)	n (%)	n (%)	x.xx
Urinary tract	n (%)	n (%)	n (%)	x.xx
If yes above, was it associated with a urinary catheter	n (%)	n (%)	n (%)	x.xx
Ear, nose and throat	n (%)	n (%)	n (%)	x.xx
Blood stream	n (%)	n (%)	n (%)	x.xx
If yes above, was it primary	n (%)	n (%)	n (%)	x.xx
Unknown focus	n (%)	n (%)	n (%)	x.xx
Other	n (%)	n (%)	n (%)	x.xx
Is there a causative microorganism identified for the infection causing sepsis				
No	n (%)	n (%)	n (%)	x.xx
Yes	n (%)	n (%)	n (%)	
Missing	n (%)	n (%)	n (%)	
Pathogens				
	n (%)	n (%)	n (%)	x.xx
	n (%)	n (%)	n (%)	

* Each site of infection is summarised separately for all participants. Therefore, it is possible that participants report more than one presumed site of infection causing sepsis.

Table 29: Baseline outcome measures comparing pre-COVID participants versus participants recruited during COVID

Outcome	Pre-COVID	During Covid	Total	P-Value	
qSOFA	N			x.xx	
	Mean (SD)	xx.xx	xx.xx		xx.xx
	Median (IQR)	xx.xx	xx.xx		xx.xx
	Missing	xx.xx	xx.xx		xx.xx

SOFA				x.xx	
	N	xx.xx	xx.xx		xx.xx
	Mean (SD)	xx.xx	xx.xx		xx.xx
	Median (IQR)	xx.xx	xx.xx		xx.xx
	Missing	xx.xx	xx.xx	xx.xx	
APACHE II				x.xx	
	N	xx.xx	xx.xx		xx.xx
	Mean (SD)	xx.xx	xx.xx		xx.xx
	Median (IQR)	xx.xx	xx.xx		xx.xx
	Missing	xx.xx	xx.xx	xx.xx	

SECTION 6 - ADVERSE EVENTS AND SERIOUS ADVERSE EVENTS

Table 30: Summary of suspected clinically relevant antibiotic related events during inpatient stay (includes events during readmissions)

	Standard care	PCT	CRP	Total	PCT vs. Standard care Adjusted estimate (95% CI)	CRP vs. Standard care Adjusted estimate (95% CI)
Number of days patients experienced a suspected clinically relevant antibiotic related event						
N	xx.xx	xx.xx	xx.xx	xx.xx		
Mean (SD)	xx.xx	xx.xx	xx.xx	xx.xx		
Median (IQR)	xx.xx	xx.xx	xx.xx	xx.xx		
Missing	xx.xx	xx.xx	xx.xx	xx.xx		
Number of patients experiencing each of the following events						
Anaphylaxis	n (%)	n (%)	n (%)	n (%)		
Gastrointestinal	n (%)	n (%)	n (%)	n (%)		
Haematological	n (%)	n (%)	n (%)	n (%)		
Hepatobiliary	n (%)	n (%)	n (%)	n (%)		
Renal	n (%)	n (%)	n (%)	n (%)		
Neurological	n (%)	n (%)	n (%)	n (%)		
Dermatological	n (%)	n (%)	n (%)	n (%)		
Cardiac	n (%)	n (%)	n (%)	n (%)		
Muscular	n (%)	n (%)	n (%)	n (%)		
Other	n (%)	n (%)	n (%)	n (%)		
Missing	n (%)	n (%)	n (%)	n (%)		
Patient experienced proven new Clostridium difficile diarrhoeal infection						
N	xx.xx	xx.xx	xx.xx	xx.xx		
Mean (SD)	xx.xx	xx.xx	xx.xx	xx.xx		
Median (IQR)	xx.xx	xx.xx	xx.xx	xx.xx		
Missing	xx.xx	xx.xx	xx.xx	xx.xx		
Patient experienced a proven new infection with a multi-drug resistant organism						
N	xx.xx	xx.xx	xx.xx	xx.xx		
Mean (SD)	xx.xx	xx.xx	xx.xx	xx.xx		

Median (IQR)	xx.xx	xx.xx	xx.xx	xx.xx	
Missing	xx.xx	xx.xx	xx.xx	xx.xx	

Table 31: Summary of suspected clinically relevant antibiotic related events post hospital discharge to 28 day follow-up

	Standard care	PCT	CRP	Total	PCT vs. Standard care Adjusted estimate (95% CI)	CRP vs. Standard care Adjusted estimate (95% CI)
Number of days patients experienced a suspected clinically relevant antibiotic related event						
N	xx.xx	xx.xx	xx.xx	xx.xx		
Mean (SD)	xx.xx	xx.xx	xx.xx	xx.xx		
Median (IQR)	xx.xx	xx.xx	xx.xx	xx.xx		
Missing	xx.xx	xx.xx	xx.xx	xx.xx		
Number of patients experiencing each of the following events						
Anaphylaxis	n (%)	n (%)	n (%)	n (%)		
Gastrointestinal	n (%)	n (%)	n (%)	n (%)		
Haematological	n (%)	n (%)	n (%)	n (%)		
Hepatobiliary	n (%)	n (%)	n (%)	n (%)		
Renal	n (%)	n (%)	n (%)	n (%)		
Neurological	n (%)	n (%)	n (%)	n (%)		
Dermatological	n (%)	n (%)	n (%)	n (%)		
Cardiac	n (%)	n (%)	n (%)	n (%)		
Muscular	n (%)	n (%)	n (%)	n (%)		
Other	n (%)	n (%)	n (%)	n (%)		
Missing	n (%)	n (%)	n (%)	n (%)		
Patient experienced proven new Clostridium difficile diarrhoeal infection						
No	n (%)	n (%)	n (%)	n (%)		
Yes	n (%)	n (%)	n (%)	n (%)		
Missing	n (%)	n (%)	n (%)	n (%)		
Patient experienced a proven new infection						

with a multi-drug resistant organism	No	n (%)	n (%)	n (%)	n (%)		
	Yes	n (%)	n (%)	n (%)	n (%)		
	Missing	n (%)	n (%)	n (%)	n (%)		

Table 32: Serious adverse events (SAE) summarised by treatment group

		Standard care	PCT	CRP	Total
SAE's					
	Number of SAE's reported	n (%)	n (%)	n (%)	n (%)
Reason Serious Adverse Event deemed serious					
	Death	n (%)	n (%)	n (%)	n (%)
	Life-threatening	n (%)	n (%)	n (%)	n (%)
	Hospitalisation or prolongation of existing hospitalisation	n (%)	n (%)	n (%)	n (%)
	Persistent or significant disability or incapacity	n (%)	n (%)	n (%)	n (%)
	Congenital anomaly/birth defect	n (%)	n (%)	n (%)	n (%)
	Other	n (%)	n (%)	n (%)	n (%)
SAE severity assessment					
	Mild	n (%)	n (%)	n (%)	n (%)
	Moderate	n (%)	n (%)	n (%)	n (%)
	Severe	n (%)	n (%)	n (%)	n (%)
	Fatal/life threatening	n (%)	n (%)	n (%)	n (%)

Table 33: Assessment of SAE's summarised by treatment group

Assessment of SAE's		Standard care	PCT	CRP	TOTAL
SAE related to trial intervention:					
	Definitely	n (%)	n (%)		n (%)
	Probably	n (%)	n (%)		n (%)
	Possibly	n (%)	n (%)		n (%)
	Unlikely	n (%)	n (%)		n (%)
	Unrelated	n (%)	n (%)		n (%)
Expectedness of SAE:					
	Expected	n (%)	n (%)		n (%)
	Unexpected	n (%)	n (%)		n (%)
Outcome of event:					
	Resolved – no sequelae	n (%)	n (%)		n (%)
	Resolved – with sequelae	n (%)	n (%)		n (%)

	Unresolved	n (%)	n (%)		n (%)
	Death	n (%)	n (%)		n (%)

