The ADAPT-Sepsis is a multi-centre three-arm randomised controlled trial with internal pilot. Participants are randomly allocated using a ratio 1:1:1 to CRP: PCT: Usual care. A computerised minimisation randomisation system was used, created by the Warwick Clinical Trials unit, to randomise participants. The randomisation allocation was made following consent processes and baseline assessments. Stratification factors were (i) sepsis severity (sepsis or septic shock), (ii) recruitment centre and (iii) surgery within the last 72 hours or not.

Primary and secondary outcomes

The primary outcomes are effectiveness outcome of total duration of antibiotics used to 28 days post randomisation and safety outcome of 28 days all-cause mortality. Secondary outcomes include escalation of care/re-admission; infection re-lapse/recurrence; dose of antibiotics; length and level of critical care stay, length of hospital stay, and 90-days all-cause mortality.

Sample size

A total sample size of 2760 would be able to detect both a mean of 1-day reduction in antibiotic use duration (using a mean antibiotic duration of 7 days, a pooled standard deviation of 6 days, 90% power, a significance level of 5%, with a 5% withdrawals rate) and a non-inferiority safety margin of 5.4 % (using a 1-sided significance level of 2.5%, 90% power and 5% withdrawal rate) assuming 28-day mortality is 15%.

Timing of final analysis

The end of the trial is defined when the last recruited participant completed 28-days follow-up post randomisation. Once all the data have been entered onto the database, the data will be fully validated and cleaned after which the database will be locked, and the final analyses will be undertaken.

Timing of outcome assessments

Primary and secondary outcome data will be collected daily from randomisation until hospital discharge. Data will also be collected post hospital discharge up to 28-days post randomisation. All-cause mortality

will be collected at 90 days using linked data. Any SAE's will also be reported up to 28 days post-randomisation.

Reporting of results

All primary and secondary clinical effectiveness outcomes will be reported in an earlier publication, with process of care and health economics outcomes reported in subsequent publications, when all the data are available.

In addition, the sub-study, RISC-sepsis will also be reported in a further publication (and has its own approved statistical analysis plan).

Statistical principles

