Confidence intervals and p-values

All statistical tests will be two-sided at the 5% significance level except for the non-inferiority safety test that will use a 1-sided significance level of 2.5%⁷. The estimate, 95% confidence interval (95% CI) and P value will be reported for each test undertaken.

Analysis populations

All analyses will be based on 'Intention-to-treat' (ITT) following ICH E9 guidelines. The participants will be analysed according to the treatment they were randomised to, irrespective of the treatment they actually received. All participants will be included in the analysis, regardless of whether they adhered to the protocol.

The Per Protocol (PP) population is usually defined as all participants who completing the study without major protocol deviations. We will identify the participants in this study who completed the study without major protocol deviations and then perform a PP analysis as secondary analysis.

Adherence and protocol deviations

The idea of site protocol adherence has been developed over a series of TMG discussions. Protocol processes have been developed through 4 key steps to help identify 'protocol adherence' and will be closely monitored during the trial. These include assessment of blood samples, production of advice, delivery of advice and the decisions taken for antibiotic treatment.

Trial population

Screening data

A detailed summary of the screening data will be presented as frequencies and percentages to describe the representativeness of the trial sample. This will include total number of hospitalised adult patients screened for eligibility, and number (percentage) of patients randomised to intervention arms.

Eligibility

The ADAPT-Sepsis trial protocol provides full details of the eligibility criteria (inclusion/exclusion criteria). The eligibility will be summarised using frequencies and percentages to describe how many patients were:

- Eligible and randomised
- Eligible and not randomised (summarising the main reasons for not randomised)
- Ineligible and not randomised (summarising the main reasons for exclusion)
-

Recruitment

A Patient Flow diagram will be used to illustrate the flow of participants throughout the trial. This will include:

- Number of patients screened for eligibility
- Number of eligible patients randomised to each intervention arm
- Number of withdrawals, died and lost to follow-up after randomisation

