	Missing	xx.xx	xx.xx	xx.xx	xx.xx
Time from first research blood sample taken for the trial to first research blood sample delivered					
	N	xx.xx	xx.xx	xx.xx	xx.xx
	Mean (SD)	xx.xx	xx.xx	xx.xx	xx.xx
	Median (IQR)	xx.xx	xx.xx	xx.xx	xx.xx
	Missing	xx.xx	xx.xx	xx.xx	xx.xx

SECTION 3 - PARTICIPANT FOLLOW-UP

Table 8: Follow-up rates throughout the trial

Treatment Group	Time-point	Total to reach time point	Completed	Withdrawn completely	Deceased	Incomplete data
Standard Care	Baseline	N	n (%)	n (%)	n (%)	n (%)
	28 days	N	n (%)	n (%)	n (%)	n (%)
	90 days	N	n (%)	n (%)	n (%)	n (%)
PCT	Baseline	N	n (%)	n (%)	n (%)	n (%)
	28 days	N	n (%)	n (%)	n (%)	n (%)
	90 days	N	n (%)	n (%)	n (%)	n (%)
CRP	Baseline	N	n (%)	n (%)	n (%)	n (%)
	28 days	N	n (%)	n (%)	n (%)	n (%)
	90 days	N	n (%)	n (%)	n (%)	n (%)

Table 9: Overall summary of withdrawals by treatment arm*

Withdrawal decision	Withdrawn from intervention only but remains on follow-up			Withdrawn from intervention completely and will not be followed-up		
	Standard care	PCT	CRP	Standard care	PCT	CRP
Participant's decision						
Consultee's decision						
Clinical team decision						
Antibiotics stopped due to futility						
Determined to require long term antibiotics (>21 days) after randomisation						
Other						

* Summary of total number of withdrawal requests i.e. participants may have more than one request

Table 10: Primary cause of death summarised by treatment arm

	Standard care	PCT	CRP	TOTAL	P-value
Sepsis or sepsis related (including organ/multi-organ failure)	n (%)	n (%)	n (%)	N	
Not related to sepsis	n (%)	n (%)	n (%)	N	

Table 11: Number of participant's withdrawing completely throughout the trial

	Standard care	PCT	CRP	TOTAL	P-value
Post-randomisation to ICU discharge	n (%)	n (%)	n (%)	N	
ICU discharge to Hospital discharge	n (%)	n (%)	n (%)	N	
Hospital discharge to 28 day follow-up	n (%)	n (%)	n (%)	N	
28 day follow-up to 90 day follow-up	n (%)	n (%)	n (%)	N	
Overall	n (%)	n (%)	n (%)	N	

Table 12: Number of deaths throughout the trial

	Standard care	PCT	CRP	TOTAL	P-value
Post-randomisation to ICU discharge	n (%)	n (%)	n (%)	N	
ICU discharge to Hospital discharge	n (%)	n (%)	n (%)	N	
Hospital discharge to 28 day follow-up	n (%)	n (%)	n (%)	N	
28 day follow-up to 90 day follow-up	n (%)	n (%)	n (%)	N	
Overall	n (%)	n (%)	n (%)	N	

Table 13: Time from randomisation to death, withdrawal and follow-up summarised by treatment arm

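### Table 12 puts p-values on deaths in periods bounded by ICU and hospital discharge, which mixes mortality with length of stay; separately, its first two rows overlap the day 28 to 90 row

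*SAP*

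**What the plan says.** The shell "Table 12: Number of deaths throughout the trial", in the participant follow-up section of the SAP's template tables, lists deaths by arm with a P-value column. Its phase rows are:

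1. "Post-randomisation to ICU discharge"
2. "ICU discharge to Hospital discharge"
3. "Hospital discharge to 28 day follow-up"
4. "28 day follow-up to 90 day follow-up"

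An Overall row follows. The SAP gives no test, denominator or rule for assigning a death to a row.

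Three other statements bear on the table.

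- Confidence intervals and p-values: "All statistical tests will be two-sided at the 5% significance level except for the non-inferiority safety test". No multiplicity adjustment is stated, so each phase p-value would be read against 5%.
- Primary and secondary outcomes: the secondary list includes "length and level of critical care stay, length of hospital stay, and 90-days all-cause mortality". Outcome definitions adds time to being fit for discharge.
- Timing of outcome assessments: "Primary and secondary outcome data will be collected daily from randomisation until hospital discharge". In-hospital follow-up is therefore not written as ending at day 28, and mortality to day 90 comes from linked data.

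The decisive mortality analysis is elsewhere. Analysis methods specifies a mixed-effects logistic model for 28-day mortality, with a risk difference compared with the non-inferiority margin. Tables 22 and 23 hold the 28-day and 90-day results.

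**The concern.** Of the limits that define the four rows (randomisation, ICU discharge, hospital discharge, day 28, day 90), two are discharge events. The SAP treats length of stay and fitness for discharge as outcomes, so it accepts that treatment may change them. If one arm leaves ICU sooner, fewer of its deaths fall before ICU discharge and more fall after hospital discharge, even when every death occurs on the same day as it would have in the other arm. A small p-value in row 1 or row 3 can then mean only that the place of death has moved, while the table invites a reading of benefit in ICU or harm after discharge.

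The second matter is separate. Rows 1 and 2 carry no day-28 limit and row 4 starts at day 28. A participant who is still in hospital at day 28 and dies there on day 35 fits row 1 or 2 and also row 4. Two programmers could fill the table differently, and the rows need not add up to Overall.

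**Working it through.** Table 12 states no figure to reproduce. The check asks how often a phase row would give p<0.05 when mortality is identical in the arms.

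**Inputs from the SAP.** Total 2760 allocated 1:1:1, so 2760/3 = 920 per arm; with 5% withdrawals, 920 × 0.95 = 874. 28-day mortality is 15%. Tests are two-sided at 5%.

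**Assumptions not in the SAP.** 90-day mortality of 20%; deaths spread uniformly within days 0-28 and within days 28-90; exponential ICU stay with mean m and exponential ward stay with mean w = 10 days, both independent of death; a two-arm two-proportion test, because the SAP names none for this table.

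**Row proportions.** The daily death fractions are a = 0.15/28 = 0.005357 and b = 0.05/62 = 0.000806.

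- Row 1 (as written, uncapped): a·m·(1 − e^(−28/m)) + b·m·(e^(−28/m) − e^(−90/m)).
- Row 3: a·[28 − I(m)], where I(m) = [m²(1 − e^(−28/m)) − w²(1 − e^(−28/w))]/(m − w). When m = w = 10, I = 20(1 − e^(−2.8)) − 28e^(−2.8).

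| Mean ICU stay | Row 1 | Row 3 |
|---|---|---|
| 10 days | 5.08% | 5.85% |
| 8 days | 4.18% | 6.47% |
| 7 days | 3.69% | 6.82% |
| 6 days | 3.19% | 7.20% |

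**Rejection rate.** z = |p1 − p2| / √(2·p̄(1 − p̄)/874), and the rate is Φ(z − 1.96) + Φ(−z − 1.96). For row 1 at 8 v 6 days, p̄ = 0.0368, the standard error is 0.0090, z = 0.00987/0.0090 = 1.10, and the rate is 19.5%.

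| Mean ICU stay, two arms | Row 1, p<0.05 | Row 3, p<0.05 |
|---|---|---|
| no difference | about 5% | about 5% |
| 8 v 7 days | about 8% | about 6% |
| 10 v 8 days | 13-15% | about 8% |
| 8 v 6 days | about 20% | about 9% |

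The 13-15% is the spread over repeated runs; the formula gives 14.7%.

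**Does the overlap cause this?** Capping row 1 at day 28 removes its second term. At 8 v 6 days the rejection rate goes from 19.5% to 19.1%. The inflation comes from the discharge boundary.

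**Size of the overlap.** The fraction of participants who die in hospital after day 28 is b times the integral from day 28 to day 90 of the probability of still being in hospital. It is 0.12% to 0.23% of participants for mean ICU stays of 6 to 10 days. Against 5% dying in that window, this is about 2-5% of day 28-90 deaths. At 874 per arm it is 1.0 to 2.0 deaths per arm.

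**Three-arm check with one p-value per row.** Take 138 deaths of 920 (15%) in every arm, so the overall p is 1.0. Let 60% of usual-care deaths and 40% of deaths in each biomarker arm fall before ICU discharge: 83, 55 and 55, mean 64.33. The sum of squared deviations is 18.67² + 2 × 9.33² = 522.7. Pearson χ² = 522.7/[64.33 × (1 − 64.33/920)] = 8.74 on 2 degrees of freedom, so p = e^(−8.74/2) = 0.013. A 10-point shift does not do this: p is 0.31 to 0.54 for a usual-care ICU share of 50% to 80%.

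**Three-arm simulation.** With other assumed stays (median 8 days each in ICU and on the ward) and both stays 20% shorter in both biomarker arms, row 1 rejects in 15.9% of trials and row 3 in 18.6%. At least one of the four phase rows rejects in 40.7%, against 16.9% with no shift; for four independent tests the expected figure is 1 − 0.95⁴ = 18.5%. The Overall row stays near 5%.

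**The case against.** The strongest reply is that this is a follow-up shell. It sits beside a withdrawals table with the same rows, and no decision rule uses its phase rows. Whether an arm is acceptable depends on the adjusted 28-day model and the risk difference against the margin. That is correct, and it limits the point to presentation. A reader might infer that the safety conclusion is at risk; the SAP gives no support for that.

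The stay differences are also assumed. The SAP gives no ICU stay and expects no particular reduction; the only effect it plans for is one day less of antibiotics. With a one-day difference in mean ICU stay (8 v 7), the error is about 8% and 6%, not far from nominal. This stands too: the mechanism is certain, but its size in this trial is unknown.

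A reader might take the overlap with the day 28 to 90 row as the source of the small p-values. It is not: capping row 1 hardly changes the rejection rate, row 3 ends at day 28 and overlaps nothing, and only 1-2 deaths per arm are affected under these stays.

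Finally, the order of the rows may mean that the authors pictured discharge before day 28, with rows 1 and 2 implicitly capped there. That is plausible, but it is not written, and daily collection runs to hospital discharge.

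None of this supplies a reason to test the phase rows. A p-value there has no clear meaning when the period it covers can differ by arm.

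**Conclusion.** The point holds as a minor one. Table 12 attaches p-values to death counts in periods whose limits treatment may move, so those p-values do not isolate mortality. Under identical mortality and the assumed exponential stays, the error in the ICU row rises from about 5% to between 8% and 20% for differences of one to two days in mean ICU stay. In the row from hospital discharge to day 28 it rises to between 6% and 9%. These rates depend on the assumed stays, on uniform death times independent of stay, on the assumed 20% day-90 mortality and on a two-arm test.

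The missing day-28 cap on rows 1 and 2 is a distinct and small counting ambiguity. The planned primary safety analysis is unaffected.

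**What to change.** In Table 12:

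- Remove the P-values from the four phase rows and show those rows as descriptive counts, with all randomised participants as the denominator.
- Cap rows 1 and 2 at day 28, so that any later death goes to row 4 wherever it occurs. The rows are then mutually exclusive and add up to Overall.
- Give between-arm mortality comparisons only for cumulative day-28 and day-90 mortality, from the models already planned for Tables 22 and 23.

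The care-phase rows can stay. Replacing them with fixed day windows is a matter of preference and is not needed.

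The cost is re-labelling one shell, using death dates that Table 13 already needs. What is lost is the display of phase-of-care p-values. Table 11 (withdrawals) has the same rows and P-value column and could be changed in the same edit.
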